4.8 Subject Replacement

If a subject receives any part of the investigation treatment, and must discontinue treatment for any reason, they will not be replaced.

5.0 STUDY PROCEDURES

5.1 General Guidelines

To be eligible for this study, the DSS Candidate must meet each inclusion criteria listed on the eligibility checklist and none of the exclusion criteria should apply. To be enrolled, the DSS candidate must have the ability to understand and the willingness to sign the informed consent form. An ombudsman must be present during the recruiting and consenting process.

The Schedule of Assessments/Events (Section 12.0) summarizes the frequency and timing of the required study assessments.

5.2 Recruitment Procedures

All DSS Candidates will be invited to participate in the proposed study. An information session will be scheduled at the beginning of each training period to provide an overview of study purpose and procedures and to give Candidates an opportunity to ask questions. Written informed consent will be obtained prior to initiating any study procedures. Consent will be obtained by study coordinator(s) not affiliated with the DSS program.

Fort Jackson has approximately 16 classes per year for DSS Candidates. These classes start every 2-3 weeks with a maximum enrollment for the year of 2,040 Soldiers or approximately 100 enrollees per class. The M-16 weapons training takes place on study days 4-14, with no training on Saturdays and Sundays. Thus, the weapons training occurs on days 4-8 and days 11-14.

Candidates will attend a recruitment briefing to introduce this research study during the first 14 days of class. The presentation will be conducted by study coordinator(s) not affiliated with the DSS training program. During recruitment briefings to a unit where a percentage of the unit is being recruited to participate as a group, an ombudsman not connected in any way with proposed research or the unit, shall be present to monitor that the voluntary nature of individual participants is adequately stressed and that the information provided about the research is adequate and accurate (DoDD 3216.02, March 25, 2002). Written informed consent will be obtained before any study assessments are performed.

Candidates will be required to use issued personal hearing protection. Every Soldier in training at Ft Jackson is issued physical hearing protection, is trained and required to use them at all times on the

weapons range. Fort Jackson makes great efforts to prevent noise-induced hearing loss by means of physical hearing protection for all Soldiers. According to the Department of Defense Instruction, 6055.12, Hearing Conservation Program (HCP), December 3, 2010, the DoD Components shall issue personal hearing protectors at no cost to all personnel working or training in hazardous noise environments. All DoD Components shall ensure proper initial fitting and supervise the correct use of all hearing protection.

We anticipate that all subjects will be using Battle Plugs provided by the Fort Jackson audiologists. Compliance with hearing protection use will be assessed and recorded each day by the study coordinator(s).

5.3 Screening

Once written informed consent has been obtained, the following assessments will be conducted.

- Review of inclusion/exclusion criteria
- Review of relevant medical history
- Review of current medication history
- Collect demographic data
- Body weight – Body weight obtained by the study coordinator(s) at enrollment will be used to determine dosing of the Study Drug.
- Urine sample to be collected from all subjects for routine urinalysis. A urine pregnancy test will be performed for all women of child bearing potential by the study coordinator(s). Pregnancy test results will be recorded.
- A blood draw for serum creatinine will be conducted prior to enrollment in order to calculate estimated GFR by the Cockcroft-Gault equation. Those subjects with an estimated eGFR < 50 will be excluded from enrollment.
- Two additional samples of blood (20-25 ml) will be collected for chemistry tests, complete blood counts, and tests of liver function, and homocysteine level.

5.4 Randomization

Enrolled subjects will be randomly assigned to receive study drug or placebo in a 1:1 ratio. Randomization scheme was developed by study statisticians and provided to KP Pharmaceutical Technology.

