10.0 STATISTICAL CONSIDERATIONS

10.1 Sample Size Justification

Based upon the results of the 2004 study at the Marine Corps Recruit Depot (MCRD), it is estimated that the rate of significant threshold shift (STS) will be approximately 38% for the control (placebo) group. A power analysis incorporating a 95% confidence level ($\alpha = 0.05$), 80% power, a 1:1 ratio (placebo to D-methionine), and a detectable difference in threshold shift rates of 30% yields a required sample size of 252 subjects for each of the two arms (placebo and D-methionine) of the study. Thus a total of 504 subjects need to complete the study. Assuming an attrition rate of 20% in each arm over the course of the study, a total of 600 subjects will need to be enrolled.

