10.2 Primary Efficacy Analysis

Two groups are planned in the randomized prospective design: the D-met and the placebo groups. The primary objectives, and their associated analyses, for this study are as follows:

1. To determine if there is a significant difference between the D-methionine and placebo treated groups in the average severity of documented side effects where severity is defined as the frequency of side effect multiplied by the intensity of the side effect. Repeated measures analysis of variance (ANOVA) will be utilized to determine significance.
2. To determine if there is a significantly reduced change in threshold hearing in each ear, adjusting for handedness, for the D-methionine group as compared to the placebo group at the tested audiometric frequencies. The tested audiometric frequencies will be 0.5, 1, 2, 3, 4, 6 and 8 kHz. Multi-way (2 groups x 7 frequencies) analysis of variance (ANOVA) with interaction effects and correction for multiple comparisons (Newman-Keuls) will be utilized to determine significance. Determination for early detection will be according to the American Speech-Language Hearing Association (ASHA, 1994) criteria of: 1) greater than or equal to a 20 dB change at any frequency, 2) greater than or equal to a 10 dB change at any 2 adjacent frequencies, or 3) loss of response at 3 consecutive frequencies where responses were obtained at baseline. To be considered significant ototoxicity, these changes must replicate within 24 hours (may be immediate) with no indication of middle ear abnormality. Subjects serve as their own controls for audiometric change, which is computed relative to baseline measures.
3. To determine if there is a significantly lower rate of STS (in either ear) for the D-methionine group as compared to the placebo group where STS is defined according to DOEHRSHC criteria as an increase of 10 dB or greater change (decrease in hearing) for the average of 2, 3 AND 4 kHz in

either ear. A significant negative STS (improved hearing) is defined as a decrease of 10 dB or greater change for the average of 2, 3 AND 4 kHz in either ear. An early warning shift STS (decrease in hearing) is defined as a 15 dB or greater change at 1, 2, 3 OR 4 kHz in either ear. Fisher's exact test will be utilized to determine statistical significance.

Secondary objective of the study is as follows:

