13.0 STUDY TIMELINE

Up to 16 Drill Sergeant School (DSS) classes are scheduled each year and each class includes approximately 100 candidates. To meet the enrollment goal of 600 subjects it is anticipated that approximately 50 subjects per class will enroll. An estimated 504 subjects are needed to complete all follow-up assessments (252 subjects per group) to detect significant differences for the primary outcome measures. The five year proposed timeline is provided in the table below. Recruitment will begin by the fourth quarter of Year 3. New DSS Training Sessions begin approximately every two-three weeks. Approximately 50 subjects are expected to enroll per session X 13 sessions. Please note that that the protocol includes enrolling the first group and completing all procedures and data collection on that group prior to additional treatment groups. The study team will then review that process before proceeding to the next group. After all procedures are documented to be flowing smoothly recruitment will proceed from each group of DSS students with classes starting every 2-3 weeks and thus, recruitment and data collection will overlap.

| | Mar 1 2011 | | | | Mar 1 2012 | | | | Mar 1 2013 | | | | Mar 1 2014 | | | | Mar 1 2015* | | | |
|------------------------------|------------|---|---|---|------------|----|----|----|------------|----|----|----|------------|----|----|----|-------------|----|----|----|
| Years | 1 | | | | 2 | | | | 3 | | | | 4 | | | | 5 | | | |
| Months | 1 | 3 | 6 | 9 | 12 | 15 | 18 | 21 | 24 | 27 | 30 | 33 | 36 | 39 | 42 | 45 | 48 | 51 | 54 | 57 |
| Site Visit | x | | x | | | x | | | x | | | | | | | | | | | |
| Study Team Meetings | x | | x | x | x | x | x | x | x | x | x | x | x | x | x | x | x | | | |
| Prepare and File IND | x | | x | x | x | x | x | | | | | | | | | | | | | |
| IRB Submission/ Approval | | | | | | x | x | x | x | x | | | | | | | | | | |
| Order Study Drug | x | | | | | | | | | | | | | | | | | | | |
| Formulate Study Drug | x | | | | | | | | | | | | | | | | | | | |
| Finalize Recruitment Plan | | | | | | | | | | | | | | | | | | | | |
| Hire Study Staff | x | | | | | | | | x | x | x | | | | | | | | | |
| Site Training | | | | | | | | | | x | x | x | | | | | | | | |
| Finalize MOP | | | | | | | | | x | x | x | | | | | | | | | |
| Pilot | | | | | | | | | | | x | x | | | | | | | | |
| Recruit/Enroll Subjects | | | | | | | | | | | | x | x | x | x | x | x | x | | |

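### Subjects enrol, fire and are tested by training class, but neither primary efficacy analysis includes class; a class term would recover modest precision at little cost

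*Combined protocol and SAP*

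**What the plan says.** **Class structure.** New classes start every two to three weeks. Weapons training falls on study days 4-8 and 11-14 (Section 5.2), and final audiometry on study days 29-32 (Section 6.3). Section 13.0 forecasts enrolment by class: "Approximately 50 subjects are expected to enroll per session X 13 sessions". It also has the first group finish all procedures before further groups are treated. Section 8.6 has adverse events reviewed at the end of each class.

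**Randomisation.** Section 5.4 gives the ratio: "Enrolled subjects will be randomly assigned to receive study drug or placebo in a 1:1 ratio". Its next sentence says that the study statisticians developed the scheme and passed it to the drug manufacturer. The scheme is not described: no block size or stratification factor is named, and none is ruled out.

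**Analysis.** In Section 10.2, objective 2 (threshold change) uses "Multi-way (2 groups x 7 frequencies) analysis of variance (ANOVA) with interaction effects", with handedness as the only adjustment named. For objective 3 (STS rate), "Fisher's exact test will be utilized to determine statistical significance". Class appears in neither, nor in the sample size calculation of Section 10.1.

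**The concern.** Subjects in one class share a firing calendar and a testing window, so their threshold shifts may resemble each other more than those of subjects from different classes. If so, a comparison that ignores class treats class-to-class differences as noise between subjects. The ANOVA then carries them in its error term. Fisher's test has no error term, but pooling the classes into one 2 x 2 table has the analogous effect of lost precision.

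If the undisclosed list is balanced within class, arm and class are unrelated by design. A test that ignores class then overstates the variance of the difference and becomes conservative. If the list is not balanced within class, chance imbalance in class membership adds variability that a class term would remove. In both cases power is at stake, not validity.

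**Working it through.** **Inputs from the documents.** Placebo rate: "the rate of significant threshold shift (STS) will be approximately 38% for the control (placebo) group" (Section 10.1). Also from Section 10.1: alpha 0.05, power 80%, 252 per arm (504 completers) and a 30% detectable difference. I read that difference as relative, 0.38 x 0.70 = 0.266, because an absolute 30 points would need only about 30 per arm. Sidedness is not stated; I take two-sided. Classes: 600/50 = 12 (Section 13.0 plans 13 sessions).

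**The plan's own figure.** n per arm = [1.96 sqrt(2 x 0.323 x 0.677) + 0.842 sqrt(0.38 x 0.62 + 0.266 x 0.734)]^2 / 0.114^2 = 263. The stated 252 is not reproduced exactly (263 is 4.4% higher). Power at 252 per arm is 78.3% by the same approximation. This gap does not affect the class question.

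**Assumed input.** No section gives the between-class variance. Write it as ICC = SD^2 / (0.38 x 0.62), where SD is the spread of class placebo rates. ICC 0.01, 0.05 and 0.10 correspond to SDs of 4.9, 10.9 and 15.3 percentage points.

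**STS power.** Simulation of 12 classes x 42 = 504 completers, 38% v 26.6%, beta-distributed class risks, common relative risk, 10,000 trials per cell, CMH without continuity correction. Power in %:

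| ICC | Allocation | Fisher (planned) | Pearson, pooled | CMH by class | Class part (CMH minus Pearson) |
|---|---|---|---|---|---|
| 0 | simple | 74.9 | 77.7 | 76.9 | -0.8 |
| 0 | blocked by class | 75.8 | 78.5 | 78.4 | -0.1 |
| 0.01 | simple | 75.6 | 78.5 | 77.7 | -0.8 |
| 0.01 | blocked by class | 75.8 | 78.9 | 79.0 | +0.1 |
| 0.05 | simple | 75.7 | 78.3 | 79.1 | +0.8 |
| 0.05 | blocked by class | 75.9 | 78.8 | 79.7 | +0.9 |
| 0.10 | simple | 75.2 | 77.7 | 79.5 | +1.8 |
| 0.10 | blocked by class | 75.9 | 78.7 | 80.9 | +2.2 |

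The standard error of one cell is about sqrt(0.78 x 0.22 / 10,000) = 0.4 points. The step from Fisher to Pearson, 2.5 to 3.1 points here, is Fisher's own conservatism and has nothing to do with class.

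A second simulation used 12 x 40 = 480 completers (600 less the stated 20% attrition) and a logit-normal class effect. It compared class-blocked allocation plus CMH with an unstratified Pearson test. The class part was about 0 at SD up to 5 points, +1 at 8-10 and +3 at 15.

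**Type I error.** In the first simulation the planned Fisher test rejects in 3.8-4.3% of null trials under simple allocation. Under class-blocked allocation it falls from 4.4% to 3.4% as the ICC rises to 0.10; pooled Pearson gives 4.6% at ICC 0.05 and 4.2% at 0.10. There is no inflation, only conservatism.

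**Many small classes.** Section 13.0 notes that enrolment continued beyond March 2015. Recruitment from the fourth quarter of Year 3 to the current version (March 2016) is about two years. At up to 16 classes a year that is about 32 classes, so 12 or 13 may be too few. With 36 x 14 = 504 completers and simple allocation (6,000 runs), pooled Pearson v CMH power was 79.4 v 76.2% at SD 0, 77.6 v 75.5% at 5, 77.8 v 76.9% at 10 and 78.4 v 79.3% at 15. Measured against the planned Fisher test, the loss was at most about 1.6 points.

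**Threshold change.** The protocol states no power for this endpoint, so take 80% as an illustration. If class explains a share r of the variance, power with a class term = Phi(2.80/sqrt(1 - r) - 1.96). For r = 0.05: Phi(0.913) = 82%. For r = 0.10: Phi(0.991) = 84%.

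**The case against.** The strongest reply is that nothing here is wrong. Subjects are randomised individually, an unadjusted primary test is a legitimate choice, and chance imbalance between classes is already covered by alpha. The documents describe uniform conditions: one site, about 500 rounds of the same weapon, one anticipated type of ear plug, one audiometer model and standard test procedures. The endpoint is change from each subject's own baseline, which removes stable differences between classes. A between-class SD of 15 points would put class placebo rates anywhere from 38 - 1.96 x 15 = 9% to 38 + 1.96 x 15 = 67%, and nothing in the documents suggests that. With many small classes, stratifying could even lose power.

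Most of this stands, and it sets the size of the point. What remains is that class is fixed before randomisation, already known for each subject and free to use. Some drift is also possible: the change log records new audiology testers and a wider age range (upper limit raised from 40 to 45). The loss with small classes is limited and can be reduced by combining adjacent classes.

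A reader might infer three stronger things that the documents do not support:
- **That the randomisation ignores class.** Section 5.4 is silent and the list is not shown; it may be blocked.
- **That class is an established source of variation in threshold shift.** It is plausible, but no section reports a difference between classes.
- **That clustering inflates the false-positive rate, as in a cluster-randomised trial.** Both arms can occur within every class, so no such design effect arises.

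**Conclusion.** The point holds as a modest matter of efficiency. Neither primary efficacy analysis uses class, and the protocol does not say whether the list does. The planned tests remain valid.

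For STS, class alone is worth about 0 points of power at a between-class SD up to 5 percentage points, about 0 to 1 at 10, and about 2 to 3 at 15. Replacing Fisher's test adds about 1 to 3 points. It would be wrong to credit the whole difference between the planned Fisher test (75-76% at 504 completers) and a class-stratified test (up to 81%) to class. For threshold change, a class term is worth about 2 to 4 points if class explains 5-10% of the variance, from an illustrative 80%.

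These sizes rest on an assumed class variance, a relative reading of the 30% difference, two-sided testing and about 12 classes.

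**What to change.** Amend Section 10.2 before unblinding:

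- **Objective 3.** Replace the pooled Fisher's exact test with a CMH test stratified by training class, without continuity correction. Report the class-stratified risk difference with its 95% CI, which also serves the plan's promise of intervals for all treatment differences. State in advance, without reference to arm, how very small classes adjacent in time will be combined.
- **Objective 2.** Add class to the ANOVA as a block factor between subjects.
- **Section 5.4.** State whether the existing list is blocked or stratified by class. This is a disclosure only.

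A mid-trial change to the allocation scheme is not recommended. The manufacturer assigns the codes and prepares individual weight-based doses (Section 7.3), so a new list would need an amendment and would leave two allocation schemes in one trial, for little gain.

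The cost is a few lines of analysis text and one variable already known for each subject. The ANOVA gives up one degree of freedom per additional class. For STS, the price is about 1 to 2 points of power if there are many small classes, allocation was not blocked by class and classes do not differ.

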5.5 Audiological Assessments: Baseline and End of Study

Subjects will be given oral and written instructions by the study coordinator(s) to avoid noise exposure for at least 24 hours prior to all audiological assessments (hearing tests). Audiological assessments will be performed using the following standardized procedures. CPT [name], AuD, a licensed audiologist and Army Hearing Program Chief at Fort Jackson, will be responsible for overseeing all testing and for

maintaining all audiologic data files for all subjects enrolled in the study. Audiological data is collected electronically via Interacoustic 629 clinical audiometers with insert earphones and TDH 39 earphones.. The threshold data will be directly exported to an Excel file and copied into the research chart.

5.5.1 Tinnitus Assessments

All subjects will be asked to complete the questionnaires at baseline and at the end of the study to determine the extent to which tinnitus has been induced by the noise exposure. The tinnitus questionnaire is modified from the Tinnitus Ototoxicity Monitoring Interview (TOMI) and the Tinnitus Handicap Index and the Tinnitus Loudness Index. The Tinnitus Handicap Inventory (THI), the most widely validated assessment tool for tinnitus, will also be used.

The TOMI (Fausti et al., 2007) and THI questionnaires, developed at the Portland, Oregon, Veteran's Administration and the Tinnitus Clinic of the Oregon Hearing Research Center have been documented in several ways. The THI was derived from detailed evaluation of over 2000 patients (Meikle 1992; Meikle et al., 1995). It is a twelve-item scale that quantifies the magnitude of tinnitus-related impairment, disability, and handicap according to guidelines established by the World Health Organization (WHO 2011; Meikle and Griest 2002). Tinnitus Handicap Inventory (THI) is the most widely validated and used tinnitus instrument (Newman et al., 1996, 2008). The THI has high internal consistency and reliability (Cronbach's $\alpha=.93$) and test-retest stability ($r=.92$) Newman et al 2008).

Subjects will be administered the tinnitus questionnaires at the time of their initial and final audiometric evaluations. Differences in the questionnaire scores will be compared pre- and post-noise in the same subject and between treatment groups. In addition to the THI, an important measure for use in evaluating potential preventive or treatment effects for tinnitus is that of magnitude scaling for the subjective loudness dimension of tinnitus. Subjective ratings for tinnitus, using a scale from 0 – 10, are well documented by a number of investigators (Meikle, 1992; Levine, 1999; Bauman and Jastreboff, 1999; Newman et al., 1996). Such ratings are quickly and easily administered, and can be efficient measures for quantifying tinnitus treatment effects. The subjective loudness rating for tinnitus captures the aversive aspect of tinnitus, in a similar manner to that of pain rating scales, which are widely used by pain experts to quantify the aversive aspect of chronic pain. It has the advantage that it does not require the subject to try and recall his or her tinnitus problems during a preceding time interval (such as a week or more), but instead can be given as an immediate and current rating of the tinnitus magnitude.

5.5.2 Otoscopy and Tympanometric Screening

Prior to each hearing test, each Soldier's ear will be examined with a Welch Allyn 3.5v MacroView otoscope to ensure that the ear canals are clear and the tympanic membranes are normal in appearance. Tympanometry will be screened in each ear using pass/fail criteria of middle ear pressure: (pass is between +110 daPa and -160 daPa) and compliance:(Pass is between .2 and 1.4 ml) using the automated Interacoustics Handheld Middle Ear Analyzer MT10.

5.5.3 Pure Tone Air Conduction Threshold/Bone Conduction Testing

Pure-tone air conduction threshold testing both at baseline and post-treatment (11-15 days after the last day of study drug/placebo administration) will be conducted utilizing the modified Hughson-Westlake procedure. Pure-tone air-conduction testing will be conducted at .5, 1, 2, 3, 4, 6, 8 kHz. Bone conduction testing will be conducted at .5, 1, 2, 3, 4 kHz if the pure tone air-conduction threshold at that frequency is greater than or equal to 15 dB HL. All testing will be conducted using standard Army test procedures using Interacoustic 629 clinical audiometers meeting all Defense Occupational Environmental Health

Readiness System – Hearing Conservation (DOEHRS-HC) and American National Standards Institute (ANSI) criteria. All testing will be conducted in a single -walled sound booth with doors closed, meeting ANSI specifications. Test equipment, test environment, procedures, and personnel will meet all relevant DOEHRs-HC, ASHA, AAA, and ANSI standards and guidelines.

Pure-tone threshold testing will be conducted using the modified Hughson Westlake procedure as follows: Initial descent towards threshold is accomplished in 10-dB steps. Beginning with the first non-response, level is increased by 5-dB for each non-response, and decreased by 10-dB after each correct detection response. Threshold is defined as the lowest level at which two responses are obtained out of three presentations on an ascending run.

Threshold shifts will also be evaluated using DoD significant change criteria and ASHA early detection criteria (1994). Significant noise-induced threshold shifts (STS) in either ear are defined by the DOEHRs-HC as an increase of 10 dB or greater change (decrease in hearing) for the average of 2, 3 AND 4 kHz in either ear. A significant negative STS (improved hearing) is defined as a decrease of 10 dB or greater change (improvement in hearing) for the average of 2, 3 AND 4 kHz in either ear. An early warning shift STS (decrease in hearing) is defined as a 15 dB or greater change at 1, 2, 3 OR 4 kHz in either ear. Subjects with an STS will undergo a final tympanogram screen to rule out middle ear pathology as a cause of the hearing loss. If they pass the tympanogram screen in both ears, they will be referred for a diagnostic audiologic follow-up exam. If they do not pass the tympanogram screen they will be referred for otologic check and then diagnostic audiological assessment.

Experimental design consists of within-subjects serial testing in which baseline standard frequency (.5, 1, 2, 3, 4, 6, and 8 kHz) audiograms are initially acquired. By comparing similar measures obtained at the end of the study period to the relevant pre-exposure measure, reliable noise-induced changes in pure-tone hearing threshold can be identified. Thus, subjects will serve as their own control for identifying hearing change, relative to their baseline evaluation.

